### **3.11.2. Baseline Visit Procedures (Week 0)**

#### **3.11.2.1. Between 6 weeks (42 days) and 14 days Prior to Baseline**

- Brain and cervical spinal cord MRI scan without and with Gd.

#### **3.11.2.2. Up to 42 days Prior to Baseline**

For patients participating in the OCT ancillary study, to be conducted only in selected countries and sites, after signature of an additional informed consent and ethics committee (EC) approval, the following assessment will be done:

- OCT evaluation (in selected sites) will be performed in all patients who signed an appropriate, EC approved informed consent form, to assess retinal thickness.

#### **3.11.2.3. Up to 7 days Prior to Baseline**

- Serum β-hCG in women of child-bearing potential (result must be available prior to the first dose at baseline).

#### **3.11.2.4. Pre-randomization**

The following procedures will be performed:

- vital signs (temperature, pulse and BP) and weight
- physical examination
- EDSS and FSS
- T25FW and 9HPT
- BICAMS, including SDMT
- LCVA
- MSWS-12
- ECG, 3 recordings 10 minutes apart before first dose
- review of changes in concomitant medications since screening visit
- inclusion/exclusion criteria confirmation, including confirmation of local radiologist that no MRI findings other than MS-related findings are present which exclude patient's participation in the study
- adverse event recording
- laboratory tests including:
  - CBC with differential

- anemia panel (blood smear, serum iron, ferritin, total iron binding capacity, folic acid, haptoglobin, interleukin [IL]-1, IL-6, interferon [IFN]- $\gamma$ , tumor necrosis factor [TNF]- $\alpha$ , and hepcidin)
- serum chemistry (including electrolytes, fibrinogen, glucose, urea, creatinine, liver enzymes, CPK, CRP, pancreatic amylase, total protein, albumin, direct and total bilirubin)
- estimated GFR
- fasting lipid profile (total cholesterol, high density lipoprotein [HDL], low density lipoprotein [LDL, measured], triglycerides)
- serum thyroid stimulating hormone (TSH), triiodothyronine (T3), and free thyroxine (T4)
- urine  $\beta$ -hCG test will be performed in women of child-bearing potential
- Blood samples for PGx assessment. If the PGx sample is not obtained at baseline for any reason, it should be collected at the next possible visit.
- blood samples for potential biomarker measures
- ascertain use of acceptable contraception

If all inclusion/exclusion criteria have been reviewed and are met, and the patient is eligible for treatment, he/she will be randomized (see Section 3.3).

### **3.11.2.5. Post Randomization**

The following procedures will be performed:

- First dose administration of the study drug.
- Vital signs (pulse and BP will be measured predose and 30 and 60 minutes after first drug administration).
- Adverse event recording will be performed upon any complaint following study drug administration (if relevant) or staff observation.
- Patients will be given all the necessary supplies and detailed instructions for administration of study drug, which will be reviewed with the patient during the visit. In addition, patients will be instructed to contact the study center if any questions or problems arise.

Patients will be instructed to contact the study site in the event of any change in their medical condition, the appearance of any adverse events, or any symptom suggestive of a relapse.

### **3.11.3. Scheduled Treatment Visits (Visits 1 to 6, Weeks 4 to 48, and Every 12 weeks Thereafter)**

Following the baseline visit, patients will return to the study center at weeks 4, 8, 12, and every 12 weeks thereafter until completion. A week is defined as  $7 \pm 2$  days.

Procedures for study completion are detailed in Section 3.11.5.

The following procedures and evaluations will be performed at these visits:

- Call IVRS/IWRS.\*
- Vital signs (temperature, pulse, BP)
- Weight\*
- Physical examination.
- ECG (weeks 4, 8, 12, 24, and every 24 weeks thereafter)
- Review concomitant medications.
- Record adverse events.
- Patient compliance (study drug accountability) and study drug dispensing.\*
- Safety laboratory tests:
  - serum pregnancy test ( $\beta$ -hCG) for women of child-bearing potential.\*
  - Urine pregnancy test ( $\beta$ -hCG) for women of child-bearing potential. In case of positive result, study drug should not be dispensed, until results of serum  $\beta$ -hCG test are available. The rest of the visit activities should be performed.\*
  - Starting from week 12 visit, between study visits, women of child-bearing potential will be provided with home pregnancy urine  $\beta$ -hCG test kits and will be instructed how to perform the test. The site staff will schedule the home test to be performed every  $28 \pm 2$  days. To verify whether the test has been performed and to record the result of the test, a mandatory phone call will be performed by the Treating Neurologist or by the site's nurse/study coordinator within 72 hours after the test was scheduled to be performed and the patient will be asked specific questions regarding the test. In case of a suspected pregnancy (positive urine  $\beta$ -hCG test result, delay of menstruation or any other reason suggesting pregnancy), the caller will ensure that the study drug has been stopped and the patient will be instructed to arrive to the study site as soon as possible (within 10 days) for further evaluations with the remaining study medications.\*
  - CBC with differential.
  - In case of hemoglobin decrease of  $>1$  g/dL from the patient's hemoglobin level at baseline:
    - patient will be re-tested to confirm decrease
    - if decrease confirmed, a thorough anemia work-up will be done including:
      - directed medical history and physical examination
      - anemia panel (blood smear, serum iron, ferritin, total iron binding capacity, folic acid, haptoglobin, IL-1, IL-6, IFN- $\gamma$ , TNF- $\alpha$ , and hepcidin) and B12

- additional investigations and follow-up per the investigator's discretion or sponsor's request
- Serum chemistry (including electrolytes, fibrinogen, glucose, urea, creatinine, liver enzymes, CPK, CRP, pancreatic amylase, total protein, albumin, direct and total bilirubin).
- estimated GFR\*
- Fasting lipid profile at week 48 and every 48 weeks until completion/ET.
- Serum TSH, T3, and free T4 at week 24 and every 24 weeks until completion/ET.
- Blood samples for potential biomarker measures will be collected at weeks 24 and 48.
- Pharmacokinetic study: blood samples for analysis of laquinimod plasma concentrations will be collected at weeks 4, 8, 12, 24 and 48.\*
- Ascertain use of acceptable contraception.\*
- All patients will undergo brain and cervical spinal cord MRI scans without Gd at weeks 24 and 48.
  - Weeks 24 and 48 MRI will be performed within 14 days of the clinical visit.
  - In case of steroid treatment, study MRI should be performed before such treatment or delayed to allow a minimum of 14 days but not more than 28 days from the completion of the steroid course.
- EDSS and FSS will be performed every 12 weeks until completion/ET visit (if applicable)
- T25FW, 9HPT, and SDMT will be performed every 12 weeks until completion/ET visit (if applicable). At week 48 and every 48 weeks thereafter, SDMT will be performed as part of the BICAMS assessment.
- mRS will be evaluated at week 72.
- BICAMS, including SDMT, will be evaluated at week 48 every 48 weeks thereafter.
- LCVA will be assessed at week 24 and every 24 weeks until completion/ET.
- MSWS-12 will be performed at week 12 and every 12 weeks until completion/ET.
- Evaluation and management of major modifiable cardiac risk factors (with referral to treatment and follow-up in suitable clinic if needed) will be performed at weeks 96 and 144.
- Ancillary studies:
  - CSF (to be performed in selected sites) will be collected from all patients who signed an appropriate, EC approved informed consent form, at week 48 (see Section 8.4.1 for further details of the assessments).

- OCT evaluation (to be performed in selected sites) will be performed in all patients who signed an appropriate, EC approved informed consent form, at weeks 48 and 96 to assess retinal thickness.

\* Patients who are discontinued from study treatment will be encouraged to continue all scheduled visits and procedures after study drug discontinuation (with the exception of procedures associated with drug dispensing and accountability, pregnancy testing, GFR testing, and pharmacokinetic sampling).

### **3.11.4. Early Termination (ET) Visit**

The following procedures and evaluations will be performed at this visit:

- call IVRS/TWRS
- patient compliance (study drug accountability)
- vital signs (temperature, pulse, and BP) and weight
- physical examination
- ECG
- review concomitant medications
- record adverse events
- safety laboratory tests:
  - serum pregnancy test ( $\beta$ -hCG) for women of child-bearing potential
  - urine pregnancy test ( $\beta$ -hCG) for women of child-bearing potential.
  - CBC with differential.
  - serum chemistry
  - estimated GFR
  - fasting lipid profile
  - serum TSH, T3, and free T4
- Ascertain use of acceptable contraception.
- EDSS and FSS
- T25FW and 9HPT
- SDMT
- LCVA
- MSWS-12
- MRI scan (without Gd): ET visit will only include MRI for patients who prematurely terminate treatment subsequent to the week 36 visit and prior to week 48. Patients who stop treatment before week 36 or after week 48 will not have MRI at ET visit. MRI will be performed within 14 days of ET visit. In case of steroid treatment, study

MRI should be performed before such treatment or delayed to allow a minimum of 14 days but not more than 28 days from the completion of the steroid course.

- BICAMS and OCT: ET visit will only include BICAMS and OCT for patients who prematurely terminate treatment subsequent to the week 24 visit and prior to week 48. Patients who stop treatment before week 24 or after week 48 will not have BICAMS and OCT at ET visit.

All reasons for ET will be documented in the source documents and the study drug termination CRF form should be recorded with the reason (the most severe) for ET.

Women of child bearing potential that performed ET should continue using 2 acceptable contraception methods up to 30 days after the last dose of oral treatment was administered. Pregnant women will perform ET visit procedures.

Moderate/strong CYP3A4 inhibitors are disallowed during the 30 days after the last dose has been administered. For information on the use of CYP1A2 substrates following laquinimod cessation, please refer to the laquinimod IB.

### **3.11.5. Completion Visit**

The following patients will be considered to have completed the study:

- Patients who participated in the study until the sponsor declared the completion of the study.

Patients who discontinue study drug but continue to attend scheduled study visits for follow-up are not considered to have completed the study.

For patients who performed a visit within the 4 weeks prior to this visit, certain activities that had already been performed do not need to be repeated. However patient compliance/drug accountability, review of concomitant medications, vital signs, ECG, and recording of adverse events must be performed in any case.

The following procedures and evaluations will be performed at this visit:

- Call IVRS/IWRS
- Patient compliance/study drug accountability
- Vital signs (temperature, pulse and BP) and weight
- Physical examination
- ECG
- Review concomitant medications
- Record adverse events
- Safety laboratory tests:
  - serum pregnancy test ( $\beta$ -hCG) for women of child-bearing potential, if applicable
  - urine pregnancy test ( $\beta$ -hCG) for women of child-bearing potential, if applicable
  - CBC with differential

- serum chemistry
- estimated GFR
- fasting lipid profile
- serum TSH, T3, and free T4
- Ascertain use of acceptable contraception.
- EDSS and FSS
- T25FW, 9HPT, and SDMT
- LCVA
- MSWS-12

Women of child bearing potential should continue using 2 acceptable contraception methods up to 30 days after the last dose of oral treatment was administered.

Moderate/strong CYP3A4 inhibitors are disallowed during the 30 days after the last dose has been administered. For information on the use of CYP1A2 substrates following laquinimod cessation, please refer to the laquinimod IB.

Study drug will be dispensed at completion visit for those patients continuing to the potential extension study.

### **3.11.6. Unscheduled Visit**

An unscheduled visit may be performed at any time during the study at the patient's request or as deemed necessary by the investigator. The date and reason for the unscheduled visit will be recorded.

The reasons for the unscheduled visit may be:

- a new adverse event or an adverse event follow-up
- change in concomitant medications
- possible relapse
- relapse follow-up
- laboratory follow-up
- study drug dispensing, accountability and/or replacement
- patient compliance
- repeat MRI scan
- other

If the visit is related to a relapse, this will be clearly indicated on the CRF and the Examining Neurologist will carry out a complete neurological evaluation (EDSS and FSS).

Mandatory unscheduled visit procedures (except for patients that perform the unscheduled visit for repeat MRI scan):

Placebo-Controlled Study – Multiple Sclerosis  
Clinical Study Protocol with Global Amendment 02 Study TV5600-CNS-20006 (ARPEGGIO)

- vital signs
- evaluation of adverse events
- review of concomitant medications
- ascertain use of acceptable contraception.

Additional clinical procedures may be performed by the Treating Neurologist to assure patient safety, and must be recorded in the source documentation.

According to the judgment of the investigator or medical monitor, the following unscheduled procedures may be performed:

- urgent safety laboratory test panel (see Section [7.3.4](#))
- collection of unscheduled pharmacokinetic blood sample
- collection of sample for potential biomarker analysis

## 4. SELECTION AND WITHDRAWAL OF PATIENTS

### 4.1. Patient Inclusion Criteria

Patients may be included in the study only if they meet all of the following criteria:

1. Patients must have a confirmed and documented PPMS diagnosis as defined by the 2010 Revised McDonald criteria (see [Appendix D](#)).
2. Baseline MRI showing lesions consistent with PPMS in either or both brain and spinal cord.
3. Patients must have an EDSS score of 3 to 6.5, inclusive, at both screening and baseline visits.a
4. Documented evidence of clinical disability progression in the 2 years prior to screening.
5. FSS of  $\geq 2$  for the pyramidal system or gait impairment due to lower extremity dysfunction.
6. Patients must be between 25 to 55 years of age, inclusive.
7. Women of child-bearing potential (for example women who are not postmenopausal or surgically sterilized) must practice an acceptable method of birth control for 30 days before taking the study drug, and 2 acceptable methods of birth control during all study duration and until 30 days after the last dose of treatment is administered. Acceptable methods of birth control in this study include: intrauterine devices, barrier methods (condom or diaphragm with spermicide), and hormonal methods of birth control (eg, oral contraceptive, contraceptive patch, long-acting injectable contraceptive).
8. Patients must sign and date a written informed consent prior to entering the study.
9. Patients must be willing and able to comply with the protocol requirements for the duration of the study.

### 4.2. Patient Exclusion Criteria

Patients will be excluded from participating in this study if they meet any of the following criteria:

1. Patients with history of any MS exacerbations or relapses, including any episodes of optic neuritis.
2. Progressive neurological disorder other than PPMS.
3. Any MRI record showing presence of cervical cord compression.
4. Baseline MRI showing other findings (including lesions that are atypical for PPMS) that may explain the clinical signs and symptoms.

---

a A capped randomization procedure will be employed to ensure that the number of EDSS 6.0 and 6.5 patients will be no more than 20% of all enrolled patients.

5. Relevant history of vitamin B12 deficiency.
6. Positive HTLV-I/II serology.
7. Use of experimental or investigational drugs in a clinical study within 24 weeks prior to baseline. Use of a currently marketed drug in a clinical study within 24 weeks prior to baseline would not be exclusionary, provided no other exclusion criteria are met.
8. Use of immunosuppressive agents, or cytotoxic agents, including cyclophosphamide and azathioprine within 48 weeks prior to baseline.
9. Previous treatment with fingolimod (GILENYA®, Novartis), dimethyl fumarate (TECFIDERA®, Biogen Idec Inc), glatiramer acetate (COPAXONE®, Teva), interferon- $\beta$  (either 1a or 1b), intravenous immunoglobulin (IVIG), or plasmapheresis within 8 weeks prior to baseline.
10. Use of teriflunomide (AUBAGIO®, Sanofi) within 2 years prior to baseline, except if active washout (with either cholestyramine or activated charcoal) was done 2 months or more prior to baseline.
11. Prior use of monoclonal antibodies ever, except for:
  - a. natalizumab (TYSABRI®, Biogen Idec Inc), if given more than 24 weeks prior to baseline AND the patient is John Cunningham (JC) virus antibody test negative (as per medical history)
  - b. rituximab, ocrelizumab, or ofatumumab, if B cell count (CD19, as per medical history) is higher than 80 cells/ $\mu$ L
12. Use of mitoxantrone (NOVANTRONE®, Immunex) within 5 years prior to screening. Use of mitoxantrone >5 years before screening is allowed in patients with normal ejection fraction and who did not exceed the total lifetime maximal dose.
13. Previous use of laquinimod.
14. Chronic (eg, more than 30 consecutive days or monthly dosing, with the intent of MS disease modification) systemic (intravenous, intramuscular or oral) corticosteroid treatment within 8 weeks prior to baseline.
15. Previous use of cladribine or alemtuzumab (LEMTRADA®, Sanofi).
16. Previous total body irradiation or total lymphoid irradiation.
17. Previous stem cell treatment, cell-based treatment, or bone marrow transplantation of any kind.
18. Patients who underwent endovascular treatment for chronic cerebrospinal venous insufficiency (CCSVI) within 12 weeks prior to baseline.
19. Use of moderate/strong inhibitors of CYP3A4 within 2 weeks prior to baseline.
20. Use of inducers of CYP3A4 within 2 weeks prior to baseline.
21. Pregnancy or breastfeeding.
22. Serum levels  $\geq 3 \times$ ULN of either ALT or AST at screening.

23. Serum direct bilirubin which is  $\geq 2 \times \text{ULN}$  at screening.
24. Patients with a clinically significant or unstable medical or surgical condition that (in the opinion of the Investigator) would preclude safe and complete study participation, as determined by medical history, physical examinations, ECG, laboratory tests or chest X-ray. Such conditions may include:
  - a. A major cardiovascular event (eg, myocardial infarction, acute coronary syndrome, decompensated congestive heart failure, pulmonary embolism, coronary revascularization) that occurred during the past 24 weeks prior to baseline.
  - b. Any acute pulmonary disorder.
  - c. A CNS disorder other than MS that may jeopardize the patient's participation in the study, including such disorders that are demonstrated on the baseline MRI.
  - d. A gastrointestinal disorder that may affect the absorption of study medication.
  - e. Renal disease.
  - f. Any form of acute or chronic liver disease.
  - g. Known human immunodeficiency virus positive status.
  - h. A history of drug and/or alcohol abuse.
  - i. Unstable psychiatric disorder.
  - j. Any malignancies, excluding basal cell carcinoma, in the 5 years prior to baseline.
25. A known history of hypersensitivity to Gd.
26. GFR  $\leq 60 \text{ mL/min}/1.73 \text{ m}^2$  at screening visit.
27. Inability to successfully undergo MRI scanning, including claustrophobia.
28. Known drug hypersensitivity that would preclude administration of laquinimod, such as hypersensitivity to mannitol, meglumine or sodium stearyl fumarate.

Special cases may need a central review of the documentation by an eligibility evaluation committee prior to baseline.

#### **4.3. Withdrawal Criteria and Procedures**

In accordance with the Declaration of Helsinki (in accordance with the applicable country's acceptance), each patient is free to withdraw from the study at any time. The investigator also has the right to withdraw a patient from the study or stop drug treatment due to any of the reasons listed in Section 4.3.1. In addition, a patient may be withdrawn from the study as described in Sections 3.6 and 5.3.

Should a patient decide to withdraw after administration of study drug(s), or should the investigator decide to withdraw the patient, all efforts will be made to complete and report all observations up to the time of withdrawal. A complete final evaluation at the time of the patient's withdrawal should be made and an explanation given as to why the patient is withdrawing or being withdrawn from the study.

The reason for and date of withdrawal from study drug treatment and the reason for and date of withdrawal from the study must be recorded on the source documentation and transcribed onto the CRF. If a patient withdraws consent, every attempt will be made to determine the reason. If the reason for withdrawal is an adverse event or a clinically significant abnormal laboratory test result, monitoring will be continued at the discretion of the investigator (eg, until the event has resolved or stabilized, until the patient is referred to the care of a health care professional, or until a determination of a cause unrelated to the study drug or study procedure is made). The specific event or test result(s) must be recorded on the source documentation and transcribed onto the CRF.

All evaluations should be performed according to the protocol on the last day the patient takes study drug, or as soon as possible thereafter.

#### **4.3.1. Patient Withdrawal Criteria**

A patient may withdraw or be withdrawn from the study for the following reasons:

- death
- patient withdrew consent
- sponsor requested patient to be withdrawn
- study terminated by the sponsor
- protocol violation
- non-compliance with study drug
- lost to follow-up/failure to return
- adverse event
- lack of efficacy (according to the investigators decision)
- pregnancy

For patients in the 1.5 mg arm who were withdrawn from study treatment, the reason will be recorded as ‘sponsor requested patient to be withdrawn’.

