#### **7.1.7. Withdrawal Due to an Adverse Event**

Any patient who experiences an adverse event may be withdrawn from the study at any time at the discretion of the investigator. If a patient is withdrawn wholly or in part because of an adverse event, both the adverse event page and termination page of the CRF will be completed at that time.

The patient will be monitored at the discretion of the investigator (eg, until the event has resolved or stabilized, until the patient is referred to the care of a health care professional, or until a determination of a cause unrelated to the study drug or study procedure is made). The investigator must inform the sponsor as soon as possible of all patients who are being considered for withdrawal due to adverse events. Additional reports must be provided when requested.

If a patient is withdrawn from the study for multiple reasons that include adverse events, the termination page of the CRF should indicate that the withdrawal was related to an adverse event. An exception to this requirement will be the occurrence of an adverse event that in the opinion of the investigator is not severe enough to warrant discontinuation but that requires the use of a prohibited medication, thereby requiring discontinuation of the patient. In such a case, the reason for discontinuation would be need to take a prohibited medication, not the adverse event.

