(new text)	
According to the judgment of the investigator or medical monitor, the following unscheduled procedures may be performed:
	Additional assessments for monitoring of cardiac risk

Original text with changes shown	New wording	Reason/Justification for change
	
 
• urgent safety laboratory test panel (see Section 7.3.4)
 
• collection of unscheduled pharmacokinetic blood sample
 
• collection of sample for potential biomarker analysis
 
	
4.3.1. Patient Withdrawal Criteria		
(new text)	For patients in the 1.5 mg arm who were withdrawn from study treatment, the reason will be recorded as 'sponsor requested patient to be withdrawn'.	Clarification due to discontinuation of 1.5 mg arm
5.2.2.1. Allowed Medications/Therapies During Study		

 
• Short-term treatment (up to 5 days) with intravenous corticosteroids will be allowed during acute-relapses, although these are rare in PPMS. The suggested treatment for a relapse will be intravenous methylprednisolone 500 to 1000 mg/day for 3 to 5 consecutive days.
 
	
 
• Short-term treatment (up to 5 days) with intravenous corticosteroids will be allowed during relapses, although these are rare in PPMS. The suggested treatment for a relapse will be intravenous methylprednisolone 500 to 1000 mg/day for 3 to 5 consecutive days.
 
	Treatment can be given for any relapses (not just acute relapses) and short-term defined.
5.2.2.2. Disallowed Concomitant Medications/Therapies During Study		
(new text)	Laquinimod is extensively metabolized predominantly by CYP3A4, and ketoconazole and fluconazole, strong and moderate inhibitors of CYP3A4, were found to inhibit the metabolism, leading to 2.5 and 3.1 fold increases in laquinimod exposure, respectively.	Rationale for disallowed medication added
5.4. Total Blood Volume		
The total amount of blood to be drawn during the study for serum chemistry, CBC, pharmacokinetic, biomarker and PGx measurements is approximately 500 550 mL/patient.	The total amount of blood to be drawn during the study for serum chemistry, CBC, pharmacokinetic, biomarker and PGx measurements is approximately 550 mL/patient.	Adjustment to allow for unscheduled tests
6.4.5. Brief International Cognitive Assessment for Multiple Sclerosis (BICAMS) Score		

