3.2.6. Tolerability Variables and Endpoints

- Proportion of patients (%) who prematurely discontinue treatment, reasons for discontinuation, and time to early termination (ET).
- Proportion of patients (%) who prematurely discontinue treatment due to adverse events, and time to ET due to adverse events.

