5. GENERAL ISSUES FOR DATA ANALYSIS

5.1. General

Due to the decision from 01 January 2016 to discontinue the laquinimod 1.5 mg dose arm, and a low study exposure at this time, the laquinimod 1.5 mg dose arm will be presented descriptively only, and will not be included in any inferential analyses.

In addition, both efficacy and safety analyses will be performed using measurements recorded during the study treatment period (i.e., data captured after treatment discontinuation will be excluded from the analyses). MRI parameters measured up to one month after the last dose of the study drug will be considered under study treatment. For all other parameters, data measured up to seven days after the last dose of the study drug will be considered under study treatment. Data captured after treatment discontinuation will be used to identify AEs which occurred after treatment termination.

Descriptive statistics for continuous variables include number, mean, and standard deviation, standard error, median, minimum, and maximum. Descriptive statistics for categorical variables include patient counts and percentages.

Summaries of abnormal and potentially clinically significant abnormal values will include all post baseline values (including scheduled, unscheduled, and early termination visits).

By-visit summaries will present all scheduled visits, including visits that appear after week 48, due to the variable treatment duration of the patients. For patients who perform an ET visit, this visit will be presented as well.

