7.6. Tolerability Variables and Analysis

Tolerability analysis will be performed only for placebo and laquinimod 0.6 mg patients and will be presented by proportion of patients (%) who prematurely discontinued treatment and reason of discontinuation (including early termination due to AEs). Additionally the time to Early Termination (ET) and time to ET due to AEs will be presented by Kaplan-Meier curves. No statistical inference will be done.

All analyses presented in the section will be repeated to include both part A and part B when the study is completed.

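### Protocol 4.3.1 fixes the recorded stop reason for 1.5 mg patients without limiting it to the arm closure, and SAP 7.6 drops that arm from descriptive tolerability without declaring it

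*Protocol*

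**What the plan says.** **How the reason for stopping is recorded.** Protocol 4.3.1 lists the permitted withdrawal reasons, adverse event among them. It then adds: "For patients in the 1.5 mg arm who were withdrawn from study treatment, the reason will be recorded as" a request by the sponsor. The sentence carries no date and no condition on cause. Three other places govern the same field or a neighbouring one:

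- Protocol 3.11.4, on the ET visit: "the study drug termination CRF form should be recorded with the reason (the most severe) for ET".
- Protocol 4.3 requires the reason for and date of withdrawal from study drug to be recorded. Where the reason is an adverse event, the specific event must also go onto the CRF.
- Protocol 7.1.7, for a patient withdrawn from the study for several reasons that include an adverse event: "the termination page of the CRF should indicate that the withdrawal was related to an adverse event".

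**How tolerability is analysed.** The objective (Protocol 2.2, SAP 2) covers tolerability of both doses against placebo. The tolerability endpoints in Protocol 3.2.6 and SAP 3.2.6 exclude no arm; one of them is: "Proportion of patients (%) who prematurely discontinue treatment due to adverse events, and time to ET due to adverse events". SAP 5.1 says "the laquinimod 1.5 mg dose arm will be presented descriptively only, and will not be included in any inferential analyses". SAP 7.6 nevertheless says "Tolerability analysis will be performed only for placebo and laquinimod 0.6 mg patients", and adds that no inference will be made. SAP section 12 lists two changes to the protocol analyses, on multiplicity and on post-ET sensitivity analyses. This is not one of them.

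**The concern.** A 1.5 mg patient who stopped for an adverse event before the closure cannot be coded under both 3.11.4 and 4.3.1 as they stand. If 4.3.1 is applied, the SAP 6.2 summary of reasons for ET could show no adverse-event stops at 1.5 mg because of a coding rule, whatever the data were. The patients who discontinued 1.5 mg have been unblinded (Protocol 3.3), so the rule ties a reason code to a known treatment arm.

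The SAP exclusion then removes the other view of the same question. Because the SAP 7.6 analysis is descriptive, the ban on inference for 1.5 mg cannot explain leaving the arm out. No planned output would give time to ET, or time to ET due to adverse events, at that dose. This is the trial's only randomised information on how long patients tolerated 1.5 mg before the sponsor stopped it.

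**Working it through.** No calculation in the plan depends on this point, so the main check is a comparison of texts. The arithmetic only sizes it.

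**1. Reason coding, case by case**

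| 1.5 mg patient | Under 3.11.4 | Under 4.3.1, read literally | Agree? |
|---|---|---|---|
| On drug at closure, no treatment-limiting event | Sponsor request | Sponsor request | Yes |
| Stopped for an adverse event before 01 January 2016 | Adverse event | Sponsor request | No |
| On drug at closure with an event that was itself leading to withdrawal | Adverse event, if judged the most severe reason | Sponsor request | Possibly not |

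The conflict is confined to the second and third rows.

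**2. Where 1.5 mg discontinuation is still reported**

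- SAP 6.2: disposition by reason for ET, no arm excluded. Exposed to the miscoding.
- SAP 8.1 and 8.3, Tables 15.88.1 and 15.88.2: adverse events causing discontinuation, by treatment group, Safety population. No arm excluded.
- Listings 16.2.7.04.1 and 16.2.7.04.2: the same events by patient.
- Protocol 7.1.2: action taken with study drug is recorded for each adverse event, separately from the termination reason.
- SAP 7.6: proportions, reasons and Kaplan-Meier curves. 1.5 mg excluded. The corresponding table (15.80) and graphs (17.15, 17.16) are labelled ITT without that exclusion, so the SAP is not consistent with itself.

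The SAP does not say whether Table 15.88 is built from the per-event action field or from the termination reason. If from the latter, the miscoding reaches that table too.

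**3. Size of the arm**

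- SAP 3.1 gives 95 patients randomised to 1.5 mg. Protocol 3.1 gives 286 randomised 1:1:1 before closure: 286 / 3 = 95.3, which agrees. Protocol 9.2 gives 280 + 95 = 375, which also agrees.
- Protocol 1.4.1.1.7 gives 35 patient-years in 191 patients at 15 November 2015. Assume even accrual to 286 by 01 January 2016 (47 days), no dropout, and one third of exposure per arm. Added exposure = (191 + 286) / 2 × 47 / 365.25 = 30.7 patient-years. Total = 65.7; per arm = 65.7 / 3 = 21.9.
- Mean exposure per 1.5 mg patient = 21.9 / 95 = 0.23 years, about 12 weeks.

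**4. Number that could be miscoded.** The documents give no adverse-event stop rate at 1.5 mg. For assumed rates of 2%, 5%, 10% and 15%, 95 × rate = 1.9, 4.75, 9.5 and 14.25, so about 2, 5, 10 or 14 patients. With all of them recoded, the disposition table would show 0/95. Read at face value, that has an exact two-sided 95% upper limit of 1 − 0.025^(1/95) = 3.8%, below three of the four assumed rates.

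**The case against.** The strongest reply is that the 4.3.1 sentence was never meant to cover earlier stops. The amendment log gives its purpose as "Clarification due to discontinuation of 1.5 mg arm". For patients taken off drug by the closure, sponsor request is the true reason. The amendment is dated 01 February 2016, and 7.1.7 has the termination page completed when an adverse-event withdrawal happens, so earlier stops should already have been coded. Nothing tells sites to overwrite those forms. This makes the narrow reading plausible, and a reader who inferred that every 1.5 mg stop is ordered to be recoded would be going too far. But the limit is not in the operative sentence, which is what a site or data manager would follow.

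A reader might also infer a direct contradiction with 7.1.7. That section speaks of withdrawal from the study, 4.3.1 speaks of study treatment, and Protocol 3.6.7 keeps the two apart. The close conflict is with 3.11.4; 7.1.7 and 4.3 only sit badly with the sentence.

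On SAP 7.6, the reply is that every remaining 1.5 mg patient stopped for one administrative reason, so a raw proportion discontinued or an uncensored curve would say nothing. The protocol synopsis also leaves descriptive tolerability statistics to the SAP, and the SAP Preface says the SAP prevails and that discrepancies will be explained in the study report. The first part is right about uncensored summaries, but censoring closure stops answers it. The second weakens the complaint about section 12 without removing it: the endpoints and SAP 5.1 still include the arm, and 7.6 gives no reason for leaving it out.

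**Conclusion.** The point holds in a limited form. The 4.3.1 sentence lacks a scope limit and, taken literally, gives a wrong reason code for any 1.5 mg patient who stopped for an adverse event. SAP 7.6 leaves the arm out of a descriptive analysis that the objective, the endpoints and SAP 5.1 all include, and this is not declared.

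It would be tempting to conclude that dose-related discontinuation at 1.5 mg is hidden. The documents do not support that while the planned adverse-event table and listings stand, subject to the open question of which field feeds Table 15.88. Nor do they support saying that the patient with a myocardial infarction at 1.5 mg (Protocol 1.4.1.1.7) was coded as a sponsor withdrawal: they do not say whether that patient withdrew, or how it was recorded.

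The size is modest and uncertain. The arm has 95 patients and about 22 patient-years, the latter resting on even accrual, no dropout and an equal split. The count of miscoded stops is unknown and may be zero; the 2 to 14 patients shown rest on assumed rates. The primary and secondary comparisons are unaffected, because 1.5 mg is outside all inference.

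**What to change.** - **Protocol 4.3.1.** Reconcile the sentence with 3.11.4, 4.3 and 7.1.7 by stating that it applies only to patients stopped by the closure who had no adverse event leading to withdrawal. Other 1.5 mg stops are coded under the general rules.
- **Data query.** Before the Part A lock, query any 1.5 mg termination form coded as sponsor request where an adverse event record shows that the drug was stopped because of the event.
- **SAP 7.6.** Add the 1.5 mg arm descriptively: proportion stopping, reason, time to ET and time to ET due to adverse events. Censor closure stops. Show it beside 0.6 mg and placebo patients randomised before 01 January 2016 and censored on that date, about (286 − 95) / 2 ≈ 95 per arm.
- **SAP 8.3 and section 12.** State which field defines an adverse event causing discontinuation, and list in section 12 any departure from the tolerability endpoints that remains.

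The cost is one protocol sentence, one query, and one extra column and curve in outputs already planned. With about 12 weeks of mean exposure the added results will be imprecise and should be labelled so.
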